10.6.1 Hypoglycemia

During the study, patients are instructed to document the presence or absence of hypoglycemic episodes or hypoglycemic symptoms in their study diary. The hypoglycemia will be reported in the specific eCRF page with onset date and time, symptoms and/or signs, the SMBG value if available, and the treatment. If the event fulfills SAE criteria, hypoglycemia will also be reported as an SAE.

Hypoglycemia is categorized according to the American Diabetes Association workgroup on hypoglycemia classification (21) and summarized in [Figure 1](#).

In addition to the threshold of ≤ 3.9 mmol/L (≤ 70 mg/dL), hypoglycemia episodes with a plasma glucose of < 3.0 mmol/L (< 54 mg/dL) will be analyzed separately.

Figure 1 - Hypoglycemia classification in Study EFC14868

*The patient is not able to treat her/himself because of the acute neurological impairment and requires another person to actively administer sugar, glucagon or intravenous glucose

PG = plasma glucose; SAE = serious adverse event

Severe hypoglycemia

Severe hypoglycemia is an event requiring assistance of another person to actively administer carbohydrate (sugar), glucagon, intravenous glucose, or other resuscitative actions. These episodes may be associated with sufficient neuroglycopenia to induce seizure, unconsciousness, or coma. Self-monitored plasma glucose values may not be available, but neurological recovery attributable to the restoration of plasma glucose to normal is considered sufficient evidence that the event was induced by a low plasma glucose concentration.

Note: “Requiring assistance of another person” means that the patient could not help himself or herself to treat the hypoglycemia. Assisting a patient out of kindness, when assistance is not required, should not be considered a “requires assistance” incident.

Any hypoglycemic event which leads to unconsciousness, coma, or seizure should also be reported as an **SAE**.

Documented symptomatic hypoglycemia

Documented symptomatic hypoglycemia is an event during which typical symptoms of hypoglycemia accompanied by a measured plasma glucose concentration of ≤ 3.9 mmol/L (≤ 70 mg/dL).

Clinical symptoms that are considered to result from a hypoglycemic episode include increased sweating, nervousness, asthenia/weakness, tremor, dizziness, increased appetite, palpitations, headache, sleep disorder, confusion, seizures, unconsciousness, or coma.

Asymptomatic hypoglycemia

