11.4.3.2 Analysis of hypoglycemia

The number (%) of patients and rate in patient years (2 types: the number of patients with events or the number of events per 100 patient-years) of all, severe and/or documented symptomatic hypoglycemia, will be summarized by treatment group respectively. In addition, documented

hypoglycemia will also be analyzed by using a threshold of plasma glucose of <54 mg/dL (3.0 mmol/L).

Their pattern of occurrence over time will also be assessed, as appropriate.

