2.1.4.1 Hypoglycemia

Hypoglycemia will be identified as events recorded on the dedicated e-CRF “Hypoglycemic event information” page, and will be categorized as follows (see study protocol for further details):

Severe hypoglycemia

Severe hypoglycemia is an event requiring assistance of another person to actively administer carbohydrate, glucagon, intravenous glucose or other resuscitative actions. These episodes may be associated with sufficient neuroglycopenia to induce seizure, unconsciousness or coma.

Self-monitored plasma glucose values may not be available, but neurological recovery attributable to the restoration of plasma glucose to normal is considered sufficient evidence that the event was induced by a low plasma glucose concentration.

Severe hypoglycemia is identified in e-CRF “Hypoglycemic event” page as those documented as, To the question “Countermeasure Administration”, ticked the option “Subject was Not Capable of Treating Self and Required Assistance”, and

To the question “Were Symptoms Present”, ticked “Yes”.

Documented symptomatic hypoglycemia

Documented symptomatic hypoglycemia is an event during which typical symptoms of hypoglycemia accompanied by a measured plasma glucose concentration of ≤ 3.9 mmol/L (≤ 70 mg/dL).

Clinical symptoms that are considered to result from a hypoglycemic episode are eg, increased sweating, nervousness, asthenia/weakness, tremor, dizziness, increased appetite, palpitations, headache, sleep disorder, confusion, seizures, unconsciousness, or coma.

Documented symptomatic hypoglycemia is identified in e-CRF “Hypoglycemic event” page as those documented as,

- To the question “Countermeasure Administration”, NOT ticked the option “Subject was Not Capable of Treating Self and Required Assistance”, and
- To the question “Were Symptoms Present”, ticked “Yes”, and
- With a plasma glucose value before countermeasure ≤ 3.9 mmol/L (≤ 70 mg/dL).

Asymptomatic hypoglycemia

Asymptomatic hypoglycemia is an event not accompanied by typical symptoms of hypoglycemia but with a measured plasma glucose concentration ≤ 3.9 mmol/L (≤ 70 mg/dL).

Asymptomatic hypoglycemia is identified in e-CRF “Hypoglycemic event” page as those documented as,

- To the question “Countermeasure Administration”, NOT ticked the option “Subject was Not Capable of Treating Self and Required Assistance”, and
- To the question “Were Symptoms Present”, ticked “No”, and

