- With a plasma glucose value before countermeasure ≤ 3.9 mmol/L (≤ 70 mg/dL).

Probable symptomatic hypoglycemia

Probable symptomatic hypoglycemia is an event during which symptoms of hypoglycemia are not accompanied by a plasma glucose determination, (but that was presumably caused by a plasma glucose concentration ≤ 3.9 mmol/L [≤ 70 mg/dL]), ie, symptoms treated with oral carbohydrate without a test of plasma glucose.

Probable symptomatic hypoglycemia is identified in e-CRF “Hypoglycemic event” page as those documented as,

- To the question “Countermeasure Administration”, NOT ticked the option “Subject was Not Capable of Treating Self and Required Assistance”, and
- To the question “Were Symptoms Present”, ticked “Yes”, and
- With no plasma glucose value before countermeasure, and

- To the question “Did this countermeasure lead a significant improvement or prompt recovery?”, ticked “Yes”.

Relative hypoglycemia

Relative hypoglycemia, recently termed “pseudo-hypoglycemia” is an event during which the patient reports typical symptoms of hypoglycemia, and interprets the symptoms as indicative of hypoglycemia, but with a measured plasma glucose concentration >3.9 mmol/L (>70 mg/dL).

Relative hypoglycemia is identified in e-CRF “Hypoglycemic event” page as those documented as,

- To the question “Countermeasure Administration”, NOT ticked the option “Subject was Not Capable of Treating Self and Required Assistance”
- To the question “Were Symptoms Present”, ticked “Yes”, and
- With a plasma glucose value before countermeasure >3.9 mmol/L (>70 mg/dL).

In addition of the threshold of >3.9 mmol/L (≤ 70 mg/dL), hypoglycemia episodes with a plasma glucose of <3.0 mmol/L (<54 mg/dL) will be analyzed separately.

Any hypoglycemic event fulfilling the criteria of a SAE or leading to unconsciousness, coma, or seizure will also be recorded as a SAE (see [Section 2.1.4.2](#)).

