2.4.5.1 Analyses of hypoglycemia

Analyses of hypoglycemia will be performed on the TEAE period as defined in [Section 2.1.4](#). For the purpose of hypoglycemia analyses during the 18-week randomized core treatment period, the TEAE period for 18-week randomized core treatment period is (1) the time from the first administration of the double-blind IMP up to 1 day after the last administration of IMP if the patient discontinued treatment on or before Visit 12 (or Day 126 if Visit 18 date is missing), or (2) the time from the first administration of the double-blind IMP to the administration at Visit 12/Week 18 (or Day 126 if Visit 12/Week 18 date is missing) if the patient remained treated beyond Visit 12/Week 18. Hypoglycemia will be classified as severe hypoglycemia, documented symptomatic hypoglycemia, asymptomatic hypoglycemia, probable symptomatic hypoglycemia or relative hypoglycemia (see [Section 2.1.4.1](#)).

The number (%) of patients with any hypoglycemia, severe hypoglycemia and documented symptomatic hypoglycemia will be summarized respectively by treatment group during the TEAE period, as well as the incidence rate in patient years. Two types of incidence rates will be presented: the number of patients with at least 1 event per 100 patient-years (calculated as the number of patients with at least 1 event / total exposure in 100 patient-years), and the number of events per 100 patient-years (calculated as the total number of events / total exposure in 100 patient-years). Note: here exposure (in days) is the duration of TEAE period, ie, duration of IMP treatment in days +1 (see [Section 2.1.4](#)).

The summary of frequency and incidence rate in patient years for severe hypoglycemia or documented symptomatic hypoglycemia will be provided as appropriate by gender (Male, Female), age group (<50, ≥50 to <65, ≥65 years), race (White, Black or African American, Asian, Other), sulfonylurea use at Week -1 (yes, no).

The number (%) of patients with at least 1 severe hypoglycemia or documented symptomatic hypoglycemia during the TEAE period, as well as the corresponding number of events, will be summarized as necessary by hour of the day for each treatment group, using the following hour intervals: ≥23:00 to <06:00, ≥06:00 to <10:00, ≥10:00 to <14:00, ≥14:00 to <18:00, ≥18:00 to <23:00.

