A KM curve will also be provided by treatment group for the time to first severe hypoglycemia or documented symptomatic hypoglycemia during the TEAE period for the entire 52-week double-blind treatment period only (see [Section 2.5.4](#)).

Documented symptomatic hypoglycemia maybe presented by ≤ 70 mg/dL (3.9 mmol/L) and < 54 mg/dL (3.0 mmol/L) respectively, as appropriate.

A listing of patients for all events reported on the dedicated e-CRF “Hypoglycemic event information” page will be provided with each category flagged (ie, severe hypoglycemia, documented symptomatic hypoglycemia, asymptomatic hypoglycemia, probable symptomatic hypoglycemia and relative hypoglycemia).

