Hypoglycemia	Safety	Follow safety guidelines Number (%) of patients with any hypoglycemia, severe hypoglycemia, documented symptomatic hypoglycemia during TEAE period of 18-week randomized core treatment period and entire 52-week double-blind treatment period, and incidence rates in 100 patient-years.		Severe hypoglycemia or documented symptomatic hypoglycemia by subgroups: race, age, gender, SU use at Week -1	KM plot time to first event of severe hypoglycemia or documented symptomatic hypoglycemia Summary of frequency/events of documented symptomatic hypoglycemia by hour during the TEAE period Documented symptomatic hypoglycemia maybe presented by <54 mg/dL (3.0 mmol/L) as appropriate.
Adverse Events	Safety	Follow safety guidelines	No	Common TEAEs by subgroups: race, age, gender, SU use at Week -1, baseline SBP, baseline eGFR	
Clinical laboratory data	Safety	Follow safety guidelines	Descriptive	No	No
Vital signs	Safety	Follow safety guidelines	Descriptive	No	No
ECG, Physical examination	Safety	Follow safety guidelines	Frequency summary	No	No

Statistical Analysis Plan

Version: Final 2.0
Lexicon Pharmaceuticals Protocol No. EFC14868

Date of Issue: 04 December 2019
Covance Study ID:000000155200

CGM SUB-STUDY ANALYSIS

Endpoint	Analysis population	Primary analysis	Supportive analysis	Subgroup analysis	Other analyses
CGM sub-study primary endpoint					
Percentage of time within the target glucose range of 70 to 180 mg/dL over 24 hours: Change from baseline to Week 19, (sotagliflozin 400 mg vs placebo)	CGM	ANCOVA (with missing values imputed by the retrieved dropouts imputation method or by washout MI method under MNAR framework): treatment, randomization stratum (HbA1c / SBP/SU use at Week -1), and country as fixed effects, and baseline CGM percentage value as a covariate	No	No	Summary statistics for observed values and changes from baseline by visit. Graphical presentations for mean changes from baseline (\pm SE) and mean values (\pm SE) by visit.
CGM sub-study secondary endpoints					

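### SAP 2.4.5.1 and Appendix C do not carry out the commitment in protocol 10.6.1 and SAP 2.1.4.1 to analyze all hypoglycemia episodes below 54 mg/dL: they specify only an optional split of documented symptomatic events.

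*SAP*

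**What the plan says.** Five places deal with the 54 mg/dL threshold.

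- Protocol 10.6.1: "hypoglycemia episodes with a plasma glucose of < 3.0 mmol/L (< 54 mg/dL) will be analyzed separately".
- Protocol 11.4.3.2: "hypoglycemia will also be analyzed by using a threshold of plasma glucose of <54 mg/dL (3.0 mmol/L". The events meant there are called documented hypoglycemia, without the word symptomatic.
- SAP 2.1.4.1: "hypoglycemia episodes with a plasma glucose of <3.0 mmol/L (<54 mg/dL) will be analyzed separately". The same sentence gives the companion threshold as above 3.9 mmol/L in one unit and at or below 70 mg/dL in the other.
- SAP 2.4.5.1: "Documented symptomatic hypoglycemia maybe presented by" the two thresholds, as appropriate.
- SAP Appendix C, hypoglycemia row: "Documented symptomatic hypoglycemia maybe presented by <54 mg/dL (3.0 mmol/L) as appropriate".

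The summaries that SAP 2.4.5.1 does require are these: "The number (%) of patients with any hypoglycemia, severe hypoglycemia and documented symptomatic hypoglycemia will be summarized respectively by treatment group". They come with two incidence rates per 100 patient-years, and none is cut at 54 mg/dL. All reported events are also listed with their category flagged.

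**The concern.** The endpoint section of the SAP and the safety section of the protocol define this measure by glucose alone. The section that tells the programmer what to produce narrows it to one symptom-based category and makes even that optional. If 2.4.5.1 and Appendix C are followed as written, the clinical study report may have no summary below 54 mg/dL. If it has one, it will leave out some episodes that meet the glucose criterion.

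This matters because every patient takes basal insulin, and sulfonylurea use is common enough to be a randomization stratum. Protocol 8.2.1.4 requires asymptomatic as well as symptomatic episodes to be entered on the hypoglycemia form. The data for the promised analysis are collected; what is missing is the instruction to tabulate them.

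**Working it through.** No sample size, power or event figure is involved, so the check compares texts and applies the SAP's own classification rule.

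**Step 1. Scope and force of each statement on the 54 mg/dL threshold**

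| Place | Episodes covered | Force |
|---|---|---|
| Protocol 10.6.1 | all hypoglycemia episodes | mandatory |
| Protocol 11.4.3.2 | documented hypoglycemia | mandatory |
| SAP 2.1.4.1 | all hypoglycemia episodes | mandatory |
| SAP 2.4.5.1 | documented symptomatic only | optional |
| SAP Appendix C | documented symptomatic only | optional |

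The three places that state the commitment are binding. The two that specify output are not, and they are narrower than protocol 10.6.1 and SAP 2.1.4.1.

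**Step 2. Which episodes the specified split can hold**

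Under SAP 2.1.4.1, an event is documented symptomatic if the assistance option is not ticked, symptoms are recorded as present, and glucose before the countermeasure is at or below 70 mg/dL. Severe events are those with assistance ticked and symptoms present. For the third category, "Asymptomatic hypoglycemia is an event not accompanied by typical symptoms of hypoglycemia but with a measured plasma glucose concentration" at or below 70 mg/dL. Four illustrative events:

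- Symptoms, self-treated, 45 mg/dL: documented symptomatic. It can enter the split.
- No symptoms, 45 mg/dL: asymptomatic. It cannot enter.
- Symptoms, assistance needed, 40 mg/dL: severe. It cannot enter.
- Symptoms, assistance needed, no glucose value: severe. It cannot be placed relative to 54 mg/dL under any wording. SAP 2.1.4.1 itself notes that a value may be lacking in severe events.

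The second and third events meet the glucose criterion in protocol 10.6.1 and SAP 2.1.4.1 but have no place in the only split that 2.4.5.1 describes.

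**Step 3. Whether another output fills the gap**

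- The summary of any hypoglycemia has no glucose cut. The five categories listed in 2.4.5.1 include relative hypoglycemia, where glucose is above 70 mg/dL, so this summary cannot stand in for one below 54 mg/dL.
- The severe hypoglycemia summary has no glucose cut.
- SAP 2.4.5 rules out abnormality summaries for plasma glucose because it is an efficacy parameter.
- The continuous glucose monitoring sub-study summarizes time and area under the curve below 54 mg/dL regardless of symptoms. It covers about 132 of about 560 patients and does not count episodes at that threshold.
- The listing shows every reported event but is not a summary by arm.

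None of these delivers the analysis promised in protocol 10.6.1 and SAP 2.1.4.1.

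**The case against.** The strongest reply is that SAP 2.1.4.1 still makes the all-episode commitment and that 2.4.5.1 does not revoke it; 2.4.5.1 only adds an optional split of one category. This stands in part. A reader might infer that the SAP as a whole drops asymptomatic and assisted episodes from any analysis below 54 mg/dL, and 2.1.4.1 does not support that. It does not settle the matter either, because the sections that specify output fail to implement the commitment and point to something narrower.

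Second, protocol 11.4.3.2 names documented hypoglycemia immediately after a sentence on severe and documented symptomatic events, and it can be read as meaning the latter category. That is fair. The clear all-episode promise is in protocol 10.6.1. On either reading 11.4.3.2 is mandatory, so the optional wording in the SAP departs from it.

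Third, a reader might infer that the most serious episodes disappear from the report. They do not. Severe hypoglycemia has its own required summary with rates, appears in the subgroup, hour-of-day and Kaplan-Meier outputs together with documented symptomatic events, and is an event of special interest. Those events lack only a 54 mg/dL cut. Nor does the hypoglycemia comparison as a whole rest on symptom reporting; that applies only to the threshold split.

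Fourth, protocol 11.4.3.2 promises summaries of all, severe and documented symptomatic events, and SAP 2.4.5.1 delivers those. The lack of a separate table of asymptomatic events is therefore not a departure from the protocol.

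Finally, scheduled glucose sampling is limited: 7-point profiles at three time points, and after Week 18 required fasting readings on three days in the week before each visit. This limits how many symptom-free low values will be found. It does not remove the commitment to analyze those that are.

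**Conclusion.** The point holds as an inconsistency within the SAP and a departure from the protocol. Protocol 10.6.1 and SAP 2.1.4.1 require an analysis of all episodes below 54 mg/dL. SAP 2.4.5.1 and Appendix C specify only an optional presentation of documented symptomatic events, and the SAP algorithm keeps asymptomatic events, and assisted events with a measured glucose, out of that category.

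Its size cannot be stated as a proportion. The documents give no share of low episodes that are asymptomatic or assisted, and any percentage would only restate an assumption. The effect is limited to descriptive safety output: no safety testing is planned, no primary or secondary efficacy inference changes, and all reported events remain in a listing. The conclusion assumes that the tables will be programmed from 2.4.5.1 and Appendix C. It should be corrected, because following those sections as written leaves a promised safety summary incomplete or absent.

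**What to change.** In SAP 2.4.5.1, replace the optional sentence with a mandatory one: for each treatment group, and for both the 18-week core period and the full 52-week period, summarize all hypoglycemia episodes with a measured plasma glucose below 54 mg/dL regardless of symptoms or assistance. Report the number and percentage of patients, the number of events, and both rates per 100 patient-years already defined in that section. Keep documented symptomatic events below 54 mg/dL as a subset row. State that events without a glucose value cannot be classified at this threshold. Make the same change in the hypoglycemia row of Appendix C.

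In SAP 2.1.4.1, correct the companion threshold so that the mmol/L and mg/dL figures agree with the category definitions in that section (at or below 3.9 mmol/L, at or below 70 mg/dL).

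The cost is a few sentences of SAP text and one additional table row with its subset. Glucose value, symptoms and assistance are already recorded on the hypoglycemia e-CRF page, so no new data collection is needed.

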2.4.5.2 Analyses of adverse events

Generalities

The primary focus of adverse event reporting will be on treatment-emergent adverse events. Pretreatment and posttreatment adverse events will be described separately.

If an adverse event date/time of onset (occurrence, worsening, or becoming serious) is incomplete, an imputation algorithm will be used to classify the adverse event as pretreatment, treatment-emergent, or posttreatment. The algorithm for imputing date/time of onset will be conservative and will classify an adverse event as treatment emergent unless there is definitive information to determine it is pretreatment or posttreatment. Details on classification of adverse events with missing or partial onset dates are provided in [Section 2.5.3](#).

Adverse event incidence tables will be presented by SOC, HLGT, HLT, and PT, sorted by the internationally agreed order for SOCs and alphabetic order for HLGT, HLT and PT within a SOC, the number (n) and percentage (%) of patients experiencing an adverse event. Multiple occurrences of the same event in the same patient will be counted only once in the tables within a treatment phase. The denominator for computation of percentages is the safety population within each treatment group.

Sorting within tables ensures the same presentation for the set of all adverse events within the observation period (pretreatment, treatment-emergent, and posttreatment). For that purpose, the table of all treatment-emergent adverse events presented by primary SOC and PT (sorted by the internationally agreed SOC order and decreasing frequency of PTs within SOCs in the sotagliflozin 400 mg group) will define the presentation order for all other similar tables unless otherwise specified. In case of equal frequency regarding PTs, alphabetical order will be used.

Analysis of all treatment-emergent adverse events

The following treatment-emergent adverse event summaries will be generated for the safety population.

- Overview of treatment-emergent adverse events, summarizing number (%) of patients with any
 - TEAE
 - Serious TEAE
 - TEAE leading to death
 - TEAE leading to permanent treatment discontinuation
- All treatment-emergent adverse events by primary SOC, showing number (%) of patients with at least 1 treatment-emergent adverse event, sorted by internationally agreed order of primary system organ class
- All treatment-emergent adverse event by primary SOC, HLG, HLT, and PT, showing number (%) of patients with at least 1 treatment-emergent adverse event sorted by the SOC internationally agreed order. The other levels (HLG, HLT, PT) will be presented in alphabetical order
- Number (%) of patients experiencing TEAE(s) presented by PT, sorted by decreasing incidence of PT in the sotagliflozin 400 mg group
- All treatment-emergent adverse events by primary SOC and PT, showing the number (%) of patients with at least 1 treatment-emergent adverse event, sorted by the internationally agreed SOC order and by decreasing incidence of PTs within each SOC in the sotagliflozin 400 mg group. This sorting order will be applied to all other similar tables, unless otherwise specified
- All treatment-emergent adverse events regardless of relationship and related to IMP by primary SOC, HLG, HLT and PT, showing the number (%) of patients with at least 1 treatment-emergent adverse event, sorted by the internationally agreed SOC order. The other levels (HLG, HLT, PT) will be presented in alphabetical order
- All treatment-emergent adverse events by maximal severity, presented by primary SOC and PT, showing the number (%) of patients with at least 1 treatment-emergent adverse event by severity (ie, mild, moderate, or severe), sorted by the sorting order defined above
- Common TEAEs (PTs with an incidence $\geq 2\%$ in any treatment group) by primary SOC, HLG, HLT, and PT, sorted by internationally agreed order of SOCs. The other levels (HLG, HLT, PT) will be presented in alphabetic order.
- Common TEAEs (PTs with an incidence $\geq 2\%$ in any treatment group) will be provided as appropriate by primary SOC, and PT and by demographic factors including gender (Male, Female), age group (<50, ≥ 50 to <65, ≥ 65 years of age), race (White, Black or African American, Asian, other), sulfonylurea use at Week -1 (yes, no), baseline SBP category

(<130 mmHg, ≥130 mmHg), and baseline eGFR category (≥30 to <60 mL/min/1.73m² [Moderate decrease in GFR], ≥60 to <90 mL/min/1.73m² [Mild decrease in GFR], and ≥90 mL/min/1.73m² [Normal]). SOC will be sorted by internationally agreed order and the PT by decreasing incidence within each SOC in the sotagliflozin 400 mg group, as described above.

- TEAEs (PTs with an incidence ≥5% in any treatment group) by primary SOC, HLGT, HLT, and PT, sorted by internationally agreed order of SOCs. The other levels (HLGT, HLT, PT) will be presented in alphabetic order.

Analysis of all treatment emergent serious adverse event(s)

- All treatment-emergent serious adverse events by primary SOC, HLGT, HLT, and PT, showing the number (%) of patients with at least 1 serious treatment-emergent adverse event, sorted by the internationally agreed SOC order. The other levels (HLGT, HLT, PT) will be presented in alphabetical order.
- All treatment-emergent serious adverse events regardless of relationship and related to IMP, by primary SOC, HLGT, HLT, and PT, showing the number (%) of patients with at least 1 treatment-emergent serious adverse event, sorted by the internationally agreed SOC order. The other levels (HLGT, HLT, PT) will be presented in alphabetical order.

Analysis of all treatment-emergent adverse event(s) leading to treatment discontinuation

- All treatment-emergent adverse events leading to treatment discontinuation, by primary SOC, HLGT, HLT, and PT, showing the number (%) of patients sorted by the internationally agreed SOC order. The other levels (HLGT, HLT, PT) will be presented in alphabetical order

Analysis of adverse events of special interest

Pregnancy and overdose will be included in overall AE summaries if any are reported. ALT increase >3 x ULN is included in laboratory PCSA summary if any.

In addition, the number (%) of patients with an AESI will be summarized by PT and by treatment group. Corresponding listings will be provided as appropriately.

Analysis of events of special interest

Cardiovascular events, bone fracture and DKA

For EOSIs that are adjudicated (ie, deaths, myocardial infarction, stroke, and unstable angina requiring hospitalization, heart failure requiring hospitalization, bone fracture, and diabetic ketoacidosis), the number (%) of patients with an EOSI positively adjudicated by CEC will be summarized by treatment group. All EOSIs sent for adjudication and/or reported by the investigators in the specific AE forms will be listed along with the adjudication outcome.

Renal events

For the EOSI renal events where selected events are adjudicated, the number (%) of patients with any renal events identified in [Table 3](#) in [Section 2.1.4.2](#) will be summarized by treatment group.

The following renal events will be listed along with the adjudication outcome if applicable, including events,

- i. recorded in e-CRF “GFR decrease”,
- ii. recorded in e-CRF “Renal Event – Dialysis”,
- iii. identified as “Renal transplant” in e-CRF “Other procedure”,

Renal death will be part of all deaths specified above.

Other EOSIs

For EOSIs that are not adjudicated, the number (%) of patients with at least one event will be summarized by treatment group and by PT (as identified in [Table 3](#) in [Section 2.1.4.2](#)).

Severe hypoglycemia will be included in the summary of hypoglycemia (See [Section 2.4.5.1](#))

AE leading to an amputation is described in the section below.

Analysis of Amputation

The number (%) of patients with amputation will be summarized by treatment group and by PT during the study (ie, regardless of on- or post-treatment). Amputation is a procedure recorded in eCRF “Other Procedures related to Amputation”. Patients who had a procedure related to amputation will be listed.

The number (%) of patients with an “AE leading to an amputation” will be summarized by treatment group and by PT. The “AE leading to an amputation” is determined by the AE identifier recorded in eCRF “Other Procedures related to Amputation” when “AE correction” is chosen as the reason for the amputation procedure.

In addition, the number (%) of patients with an “AE potentially leading to an amputation” will be summarized by treatment group and by PT (as identified in [Table 3](#) in [Section 2.1.4.2](#)). The associated list will be provided as well, with patients who had an amputation procedure flagged. “AE potentially leading to an amputation” represents the condition that commonly precedes the amputation procedure, but not in all cases an amputation has occurred.

Analysis of pretreatment and posttreatment adverse events

- All pretreatment adverse events by primary SOC and PT, showing the number (%) of patients with at least 1 pretreatment adverse event, sorted by the internationally agreed SOC order and decreasing incidence of PTs within each SOC in the sotagliflozin 400 mg group

- All posttreatment adverse events by primary SOC and PT, showing the number (%) of patients with at least 1 posttreatment adverse event, sorted by the internationally agreed SOC order and decreasing incidence of PTs within each SOC in the sotagliflozin 400 mg group

Listings

Supportive AE listings will be provided for all AEs, SAEs, AEs leading to treatment discontinuation and/or death, and EOSI as appropriate. Listing of all AEs, SAEs and AEs leading to treatment discontinuation and/or death, sorted by treatment, patient identification and onset date, will include at least the following information: treatment, patient identification, country, age, gender, race, BMI, primary SOC, PT, reported term, onset date, study day (relative day to the start date of double-blind treatment), AE duration, duration of exposure, intensity, corrective treatment, action taken with IMP, date of treatment discontinuation (if relevant), relationship to IMP or NIMP, outcome, date of death (if any), seriousness, seriousness criteria, and AE status (“E” for a TEAE; and “P” for an on-study post-treatment AE).

